**Figure 1: Patient Arms**

**Figure 2: Intervention by Patient Arm**

5.2 Study duration

The study is expected to begin in November 2020 and take 12 months to complete.

### *5.3 Target population*

125 patients with incurable lung and gastrointestinal cancer treated at the University of Pennsylvania Health System's Perelman Center for Advanced Medicine (PCAM).

### *5.4 Accrual*

The study sample will be drawn from patients who receive their cancer care from a GI or lung oncologist at the University of Pennsylvania's Perelman Center for Advanced Medicine (PCAM). We aim to enroll 125 patients. We anticipate enrolling these 125 patients over 6 months at a rate of 4 patients per week, a small fraction of the number of eligible patients with in-person or telemedicine visits at PCAM each week. A summary of recruitment mechanisms is found in Section 6 (Subject recruitment).

### *5.5 Key inclusion criteria*

Patients must meet the following criteria to be eligible for the study:

1. English-speaking
2. Have a diagnosis of incurable or Stage IV lung or gastrointestinal cancer
3. Receive primary oncology care with a thoracic or gastrointestinal medical oncology specialist at the Perelman Center for Advanced Medicine (i.e. does not have a local oncologist that provides cancer care, including other UPHS clinic sites)
4. Currently receiving or planned receipt within 2 weeks of IV chemotherapy (see exclusions below)
5. The patient has a smart phone that can receive SMS text messages and has blue-tooth capability that can connect to Fitbit.

### *5.6 Key exclusion criteria*

Patients will be excluded if any of the following criteria apply:

1. Age < 18 years
2. Patients has used a wheelchair, been bedbound or is unable to walk without assistance from other people every day for the past 7 days (patients are not excluded for the use of walkers or canes)
3. Patients who are receiving checkpoint inhibitor monotherapy, IV targeted therapy monotherapy (e.g. panitumumab) or oral tyrosine kinase inhibitors
4. Patients who receive chemotherapy infusions at another UPHS site or outside of UPHS or whose primary oncologist is not in thoracic or gastrointestinal oncology groups at PCAM. Notably, patients who receive part of their chemotherapy regimen at home will still be allowed to enroll.

5. Lung cancer patients enrolled in an ongoing palliative care clinical trial that may lead to better communication regarding symptoms and functional status.
6. Clinician concerns about behavioral health issues that may prevent engagement with text message prompts
7. Are enrolled in another interventional clinical trial (as clinical trials often have a substantial symptom-reporting structure; non-interventional clinical trials are permitted e.g. trials that just involve blood tests)

## **6. Subject recruitment**

The recruitment and onboarding process can be conducted either in-person or remotely (depending on restrictions in place due to the COVID-19 pandemic). Upon trial initiation, we will obtain permission from GI and lung oncology clinicians to approach their patients regarding this trial. A clinical research coordinator (CRC) will conduct brief chart reviews of patients scheduled to see a GI or lung oncologist at PCAM to identify patients that meet eligibility criteria. The CRC will then electronically notify clinicians prior to their scheduled appointments with these patients to confirm eligibility and inform them that they will be approaching the patient. When approaching potentially eligible patients, the CRC will wear appropriate protective equipment and will meet the patient in the private clinical patient room or the private chemotherapy infusion room to describe the trial and determine eligibility. CRCs may also contact potentially eligible patients by phone and/or email to describe the trial and determine eligibility. The CRC will use a script developed by the research team when approaching patients in-clinic or by phone (**Appendix A**) or electronically based on template language provided by the Office of Clinical Research (**Appendix B**). After eligibility is confirmed, interested participants will be directed to the online Way to Health (W2H) portal to review and provide informed consent, enroll in the study, and complete baseline questionnaires. The CRC will also inform clinicians regarding patient enrollment and ask the clinician to estimate the patient's Eastern Cooperative Oncology Group performance status. The CRC will assist with setting up W2H and their Fitbit device in-person or by phone or a virtual meeting (a support partner will be encouraged to attend).

## **7. Subject compensation**

Patients in arms a, b, and c will be compensated with a \$25 payment for completing their first utility survey at 3 months after enrollment and another \$25 payment for completing their second and final utility survey at 6 months after enrollment. Patients in arms b and c will be permitted to keep the Fitbit as part of the trial.

## **8. Study procedures**

### *8.1 Patient Consent*

Upon recruitment, the research coordinator will contact potential participants to confirm their eligibility and explain the study's objectives, duration and requirements. Individuals who are interested in learning more about the study will be directed to the online W2H portal. Upon reaching the portal, potential participants will be led through an automated online informed consent process (**Appendix C**). The consent document will be divided into sections, requiring the click of a button to advance from one section to the next. This will help ensure that participants read the consent form thoroughly by breaking down the form into manageable blocks of text. Successive screens will explain the voluntary nature of the study, the risks and benefits of participation, alternatives to participation, and the process for study withdrawal. The consent form will clearly state that the weekly electronic symptom surveys and step data will be shared with the patient's care team via the electronic medical record, whereas all other information collected during the study will remain confidential, available only to the study team and with appropriate privacy protections in place.

On the final consent screen, a clearly delineated button will enable patients to agree (or not) to participate in the study. Additionally, a platform electronic signature using a finger on a touch screen of a mobile phone will be required. Those who elect not to participate will be asked to grant permission (or not) for the study team to collect limited data from them. An abbreviated Study Decline Consent form will be utilized for this purpose, similarly requiring the click of a clearly delineated button to agree (or not) to limited data collection, as well as a platform electronic signature (**Appendix D**).

Upon agreeing to participate in the study and clicking the appropriate button, participants will have consented to enroll in the study. Participants will then be prompted to complete an online enrollment questionnaire asking for basic demographic information (e.g. age, sex, race, education, computer experience- **Appendix E**). Additional patient characteristics (e.g. Eastern Cooperative Oncology Group performance status, Charlson comorbidity score), tumor characteristics (e.g. histology), and treatment characteristics (e.g. line/type of therapy) will be abstracted from the medical record at the time of enrollment. The patients will also receive a sample survey via text message that mimics the weekly PRO survey they will receive, but the sample survey results will be discarded. The sample will be clearly labeled to indicate that the response are not monitored.

Those who elect not to participate but consent to limited data collection, will be asked to fill out a very brief online questionnaire, asking basic demographic information, computer/mobile phone experience, and reason(s) for not wanting to participate in a de-identified manner (**Appendix F**).

After enrolling, participants will be provided with details regarding how to contact the research team via email or phone at any time if they subsequently wish to withdraw from the study or have other study-related concerns.

We request a waiver of informed consent for consenting physicians. Prior to the start of the trial, we will obtain permission from all GI cancer and lung cancer clinicians at the Perelman Center for Advanced Medicine to approach their patients. As the study does not limit clinical care in anyway (e.g. in contrast to a therapeutic intervention trial, where receipt of a treatment might make the patient ineligible for other therapies), clinician consent is not needed. The intervention simply provides additional information that clinicians can use (or choose not to use) to inform routine care of the patient.

### *8.2 Clinician Consent*

Prior to launching the study, the research team will present a brief slide deck at a monthly meeting for relevant PCAM providers including the GI oncology and thoracic oncology tumor board meetings. The PIs will go over the study plan including the design, background, and outcomes. The investigators will obtain verbal consent from all providers to 1) recruit patients into this study and 2) answer a utility survey at 3 and 6 months following enrollment for each patient.

### *8.3 Procedures*

#### **Setting up patients**

The CRC will assist the patient in setting up a W2H account that will deliver the weekly PRO surveys and collect Fitbit data. The CRC will be responsible for confirming the patient receives their Fitbit device at their infusion treatment (typically, the CRC will give this directly to the patient in-person, but they can be dropped off beforehand if there are restrictions in place due to the COVID-19 pandemic). Patients will be shown how to use their Fitbit and link it to their W2H account, then being asked to authorize the device to electronically transmit device data to the study database. Participants will be instructed to wear the Fitbit device as much as possible, including during sleep, for the duration of the study. Participants will be told that they need to sync their wearable device with their smartphone in order for data to be transmitted to the study team. Participants will receive regular text message reminders prompting them to wear and sync their devices.

#### **Remote-PROs**

*Timing.* On Monday of every week, patients will receive a series of text messages to solicit patient-reported symptoms.

*Mechanism of delivery.* Text messages will be sent via the W2H platform. Patients will receive the surveys in the form of text messages on their phone.

*Content of the text messages.* The text messages will inquire about seven symptoms, requesting a response rating the patient's response. The seven symptoms have been selected by lung and GI oncology clinicians at PCAM from a list of twelve validated symptoms from the National Cancer

Institute's Common Terminology Criteria for Adverse Events and will be scored on a five point scale from 0 (no present) to 4 (disabling). The patients will also receive a question asking about their activity level over the prior month (**Appendix G**).

*Who may respond:* During trial enrollment, the patient will be instructed to answer the text messages. However, a caregiver may respond for the patient if the patient needs assistance.

*Safety.* PRO data will be shown to clinicians in the PROStep Dashboard (see below) and will not be monitored in real time by a clinician. All study participants will be provided with the research coordinator and principle investigator's email and phone number to contact with any questions or study-related concerns. Participants will be educated at the outset and reminded throughout the study, both verbally and in writing, that the symptom-reporting tool is intended for research purposes only. If a participant feels that their symptoms warrant more urgent evaluation, s/he will be instructed to call their provider in the usual fashion. The principal investigator will be available at all times, should physician escalation be necessary.

A severe symptom ( $\geq 3$ ), or any abrupt change in symptom severity ( $\geq 2$ ), will trigger an alert to the participant's care team via an EPIC message to the attending clinician's symptom pool inbox, whose clinicians will be empowered to intervene at their discretion. Possible interventions might include a telephone call, prescription medication, home care visit, same-day office visit, urgent care, and/or acute care referral. The CRC will review all text message responses each non-holiday weekday for other responses that may warrant closer attention by clinical teams and will call the primary oncology team or send an EPIC message, as appropriate. The CRC can call the study investigators or primary oncology teams at any time to determine whether a text message requires further action.

Until 30 PRO surveys have been sent (e.g. 10 patients for 3 weeks, or 3 patients for 10 weeks), the study investigators and CRC will have a weekly meeting to review the number of responses that cross the alert threshold hold, any text message responses and identify any changes to the protocol that may be needed to ensure the adequacy of this safety mechanism. After this period, the CRC will discuss any concerning text messages to the study investigators.

Patients may opt out of the text message intervention at any time by responding to a W2H text message with the phrase "Stop". The CRC will contact the patient by the next non-holiday weekday to determine whether the patient would like to 1) resume receiving the text messages (in which case they will be reactivated), 2) continue in the trial without receiving the text messages, or 3) withdraw from the trial.

If a patient in the intervention group does not respond to two weekly surveys the CRC will contact the patient to inquire about obstacles to participation (e.g. mobile phone has changed, patient does not wish to participate, etc). Patients will be provided with the CRC's email and phone number to contact with any questions.

## **Step monitoring**

At enrollment, the CRC will instruct patients on how to wear the Fitbit device and periodically sync the device with their phone to send step data to W2H, as described above. As the device has a 5 day memory, patients will receive a reminder to sync Fitbit twice per week as well as two days before a clinic visit unless the data was synchronized in the prior 24 hours. If patients have no step data transmitted for a two week period, the CRC will contact the patient. Note that while step data will be collected to assess activity, GPS data will not be collected or used in this study.

## **Presenting PROStep Dashboard to clinicians**

The study team will provide an updated PROStep Dashboard (**Appendix H**) to lung or GI oncology clinicians for each patient enrolled in the intervention arms prior to their appointments. W2H will generate the dashboards and the study team will physically deliver it to their office or touchdown space or send electronically. The Dashboard will include:

1. Home-based PRO report, including the weekly survey results for each question in tabular and graphical form
2. Step data report, including a summary of number of daily steps in graphical form (with rolling weekly averages) and weekly averages in tabular form
3. A list of all acute care utilization in the UPHS system in the prior 6 months including,
  - a. Oncology Evaluation Unit visits
  - b. Emergency department visits
  - c. Inpatient admissions
4. Whether the patient has had an outpatient palliative care visit
5. Whether the patient has had a documented Serious Illness Conversation

## **Active nudge text feedback**

Intervention patients in arm c will receive text feedback describing worsening or severe symptoms collected from their remote PRO questionnaires (i.e. “Your following symptoms are severe or have gotten worse:”) and their step count (“Your Fitbit step count compared to last week is worse.”). They will also receive an “active nudge” question on their upcoming visit (i.e. “Do you plan on discussing these symptoms with your oncologist at your upcoming visit? Type "1" if you plan to discuss them; Type "2" if you do not plan to discuss them.”).

## **Clinician surveys**

At 3 and 6 months after patient enrollment, the patient’s oncology clinician team (the attending oncologist and associated advanced practice providers that had an encounter with the patient during the study period) will receive an emailed survey to assess the clinicians’ perspectives on the utility of the PROStep Dashboard for the specific patient (**Appendix I**). Clinicians will be surveyed for each intervention patient (arms b and c) enrolled in the study including patients who

disenroll early but were enrolled for at least 4 weeks of the enrollment period for the upcoming survey.

### **Patient surveys**

At 3 and 6 months after enrollment, all patients (arms a, b, and c) will receive a text message with a link to a survey to assess the patients' perspectives (**Appendix J**). Patients are eligible to receive these surveys if they are enrolled in the study for a minimum of 4 weeks.

### **Patient exit interviews**

Upon exiting the trial, all intervention patients (arms b and c) will receive a brief exit interview to gather feedback. The CRC will conduct these interviews, and they will consist of the following questions:

1. *Overall, what did you think of the intervention?*
2. *What parts were the most helpful?*
3. *What parts were not helpful?*
4. *What should we change?*
5. *How often do you have your smart phone in your pocket when you walk around?*
  - *Never*
  - *Rarely*
  - *Sometimes*
  - *Most of the time*
  - *Always*

### **Data collection**

Patient data for outcome determination will be obtained from W2H (for home-based PROs and Fitbit device data), Penn Data Store and Clarity (Epic's data reporting database, for the remaining outcomes).

## **9. Analysis plan**

For each primary outcome, we will compare the mean scores from the survey questions at 6 months (see section 3.1) for all 3 groups (2 intervention, 1 control) using a Kruskal-Wallis test with  $p < 0.05$  indicating statistical significance. If the result is significant, we will use the Tukey's honestly significantly difference (HSD) test to test pairwise comparisons. If the outcomes for any arm are skewed (not normally distributed), we will use log-transformation before applying all tests. For

clinicians who have completed a 3-month survey for a specific patient, but do not complete a 6-month survey for that patient, we will apply their 3-month survey responses in place of their missing 6-month survey for analysis for that specific patient. For example, if Clinician A completes a 3-month survey for Patient A, but not a 6-month survey, we will use the results from their completed 3-month survey in its place for Patient A (but not for other patients). That said, we will do a sensitivity analysis only using the coded 6 month analyses (complete case analysis).

We will repeat this analysis for the secondary outcome of composite survey score at 3 months. For patients who exit the study early, we will attempt to administer their next survey and use that assessment. These will be administered if patients have been enrolled for a minimum of 4 weeks of the enrollment period leading up to their following survey. For example, if a patient disenrolls 4 weeks after receiving their 3-month utility survey, they will be eligible for their 6-month survey whereas a patient who dis-enrolls at 3 weeks will not). If a patient dies or is otherwise unable to complete a survey, they will be omitted from the analysis for the relevant outcome. For patients who disenroll from the trial for any reason (voluntary, death, etc.), but meet this 4 week threshold, their clinicians will receive a utility survey. To assess whether responses in 3-month to 6-month surveys differ across arms, we will run an analysis of covariance (ANCOVA) model with the baseline score and arms as covariates, and change of score as the dependent variable.

We will use descriptive statistics to compare the secondary outcomes of adherence rates between the two intervention groups and trends in PROstep data. We will use Kruskal-Wallis tests for continuous outcomes and chi-square tests for categorical variables to compare these outcomes between all arms at 3 and 6 months.

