## 3. Outcomes

### *3.1 Primary outcome*

Patient utility surveys will use a 5-point Likert scale for responses scored 1-5. The two co-primary outcomes will compare the scores for the following two questions, **measured at 6 months (or 3 months if the patient did not complete their 6 month survey)**, between **intervention patients** (Arms B + C) and **control patients** (Arm A).

- How well do you feel your oncology team understands your symptoms (e.g. nausea, vomiting, weight loss, etc.)?
- How well do you feel your oncology team understands your activity level and ability to function?

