### *3.2 Secondary outcomes*

The following secondary outcome will compare the same questions:

- **Measured at 3 months**, between **intervention patients** (Arms B + C) and **control patients** (Arm A).

We will compare cumulative adherence for patients in the intervention group (arm B and arm C). Each week, adherence will be defined as each week where the patient submits the weekly survey (i.e. adherence to PRO) and has step data for 4 of 7 days of the week (i.e. adherence to Fitbit platform), divided by the total number of weeks that the patient is enrolled in the trial.

- Comparison of mean patient adherence at three months for patients in arm B vs arm C
- Comparison of mean patient adherence at six months for patients in arm B vs arm C

We will analyze trends in the PROStep data (PRO surveys and Fitbit step data).

- Comparison of PRO scores between patients in arm B vs. arm C. These will be measured using mean and median composite symptom scores as reported by patients in their PRO surveys. The composite score is the sum of the scores for each domain in the PRO survey, and the mean or median composite symptom score is the mean or median of all composite scores collected during the study.
- Fitbit step data will be measured using mean daily step counts for all days in which Fitbit data is collected. Days where the patient does not have Fitbit data will be excluded from these calculations.

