### 3.3 Exploratory outcomes

- The following exploratory outcomes will make the following comparisons for responses to the two questions in the primary outcomes:
  - Measured at 6 months (or 3 months if the patient did not complete their 6 month survey)
    - Between Arm B and Arm A
    - Between Arm C and Arm A
    - Between all Arms.
  - Measured at 3 months:
    - Between Arm B and Arm A
    - Between Arm C and Arm A
    - Between all Arms.
- Number of palliative care consults
- Number of documented advanced care planning (ACP) notes
- Number of documented serious illness conversations (SIC)
- Correlation between step, heart rate, distance, pace, elevation and sleep data trends, patient reported outcomes, patient and clinician ECOG assessment, and patient hospitalization and survival

- We will report descriptive statistics for the remaining questions on the patient utility surveys (mean and standard deviation) followed by t-tests between each individual arm and between all intervention patients (Arms B + C) and control patients (Arm A). Patient utility surveys include the following (the intervention arms receiving additional questions):
  - How well do you feel that your oncology team has addressed your symptoms?
  - How well do you feel that your oncology team has addressed your activity level and ability to function?
  - I feel that the PROStep data prompted better communication with my oncology team about my symptoms. **(arm b and arm c)**
  - I feel that the PROStep data prompted better communication with my oncology team about my activity level. **(arm b and arm c)**
  - My oncology team has discussed the PROStep data during my appointments. **(arm b and arm c)**
  - I feel that the PROStep data changed how my oncology team addressed my symptoms and/or ability to function. **(arm b and arm c)**
  - I feel that the PROStep data changed my oncology team's treatment of my cancer, such as decisions to start, continue, or stop cancer treatments like chemotherapy. **(arm b and arm c)**
  - I feel that the PROStep data triggered discussions with my oncology team about my prognosis or goals of my cancer care. **(arm b and arm c)**
  - I feel that regularly wearing my Fitbit is burdensome. **(arm b and arm c)**
  - I feel completing my weekly symptom surveys is burdensome. **(arm b and arm c)**
  - On a scale of 0-10, how likely is it that you would recommend PROStep to other patients with cancer? **(arm b and arm c)**

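### Section 9 does not test the pooled B + C versus A contrast that Section 3.1 makes primary, and no rule says whether one or both co-primary questions must succeed

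*Combined protocol and SAP*

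**What the plan says.** Section 3.1 (Primary outcome): "The two co-primary outcomes will compare the scores for the following two questions". It fixes the contrast as two groups, "between intervention patients (Arms B + C) and control patients (Arm A").

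Section 9 (Analysis plan) handles each question separately: "For each primary outcome, we will compare the mean scores from the survey questions at 6 months". It does so, however, "for all 3 groups (2 intervention, 1 control) using a Kruskal-Wallis test", with p<0.05 as the threshold. It continues: "If the result is significant, we will use the Tukey's honestly significantly difference (HSD) test to test pairwise comparisons". If any arm's scores are skewed, they are to be log-transformed before testing; 'skewed' is given no criterion.

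Section 3.3 (Exploratory outcomes): "The following exploratory outcomes will make the following comparisons for responses to the two questions in the primary outcomes". The list that follows includes B versus A, C versus A and all arms together, at the same 6-month (or 3-month) timing. Section 3.3 also plans t-tests of B + C versus A, but only for the remaining survey questions.

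The only hint of combining questions is for a secondary outcome. Section 9 says "We will repeat this analysis for the secondary outcome of composite survey score at 3 months", while Section 3.2 says of the 3-month analysis "The following secondary outcome will compare the same questions". The composite defined in Section 3.2 belongs to the weekly symptom survey, not to this one.

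**The concern.** There are two separate gaps.

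**The contrast.** The comparison called primary in Section 3.1 has no test in Section 9, and the comparison tested in Section 9 is exploratory in Section 3.3. Tukey pairs (A-B, A-C, B-C) do not fill the gap, since none of them is pooled B + C against A. If the three-group and pooled tests disagree, the plan does not say which is the primary result.

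**The success rule.** Each question gets its own verdict at p<0.05. Nothing orders the two questions, adjusts across them, or says whether one or both must succeed. Tukey's method covers pairs of arms within one question, not the two questions. If only one reaches p<0.05, whether the trial met its primary objective could be decided after the data are seen.

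**Working it through.** The documents give no family-wise error rate, power or sample-size derivation, so there is no stated figure to reproduce.

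**Inputs from the documents.** Two co-primary questions, each on a 1-5 scale (Section 3.1); p<0.05 for each (Section 9); 1:1:1 allocation (Section 5.1); 125 patients (Section 5.4), so 125/3 is about 42 per arm.

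**Assumptions, none of them in the documents.** Between-question correlation 0.3-0.8; response probabilities 5/10/25/35/25% for scores 1 to 5; a true shift of 0.6 SD on the underlying scale; 28 per arm if two-thirds respond. The error rates and equal-shift power figures use 200,000 simulated trials per setting, except the log-transformed Tukey route.

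**1. Either question counts, no true effect.** For independent questions: 1 - (1 - 0.05)² = 1 - 0.9025 = 9.75%. For correlated questions: P(either) = 0.05 + 0.05 - P(both).

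| Correlation | P(both), normal theory | P(either) = 10% - P(both) | Simulated either, three-group | Simulated either, pooled rank test |
|---|---|---|---|---|
| 0.3 | 0.49% | 9.51% | 9.45% | 9.60% |
| 0.5 | 0.93% | 9.07% | 8.92% | 9.02% |
| 0.8 | 2.19% | 7.81% | 7.94% | 7.94% |

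The simulated columns are at 42 per arm; at 28 per arm the results are similar (7.8-9.4%). The two tests agree closely, so the excess over 5% comes from the missing rule across questions and not from the choice of test.

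**2. Either question counts, and a Tukey intervention-control pair is also needed.** On raw scores the risk is 4.6-5.6%. The assumed responses are skewed, so Section 9 could call for the log step; the risk is then about 3.5-4.2%. Kruskal-Wallis uses ranks and is unaffected by the log; Tukey is affected. The response shape matters too: a flat distribution gave up to 6.3% on raw scores. Section 9 does not make a Tukey pair a condition of success.

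**3. Both questions required.** The risk is 0.4-2.2% when neither question has an effect. It rises to 5.0% when one has a large true effect and the other has none, which is the ceiling.

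**4. Holm on the pooled test.** The risk is 3.9-4.8% at correlations 0.3-0.8.

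**5. Power for one question, 42 per arm, unadjusted.**

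| Shift in B / C (SD) | Three-group | Pooled |
|---|---|---|
| 0.6 / 0.6 | 73% | 82% |
| 0.3 / 0.6 | 60% | 58% |
| 0.2 / 0.6 | 61% | 48% |
| 0 / 0.6 | 73% | 29% |

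The pooled test is stronger when B and C shift equally. The order reverses as their effects diverge.

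**The case against.** **Co-primary commonly means that both must succeed.** On that reading the error is at most 5% and nothing is inflated. This stands as a possible reading, but the text does not state it, and Section 9 attaches significance to each outcome separately. The contradiction between Sections 3.1, 9 and 3.3 remains on either reading.

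**This is a feasibility study.** The abstract says so, and strict error control over two survey items can be called a preference. That limits the request to wording and is no reason for a larger sample. But the plan itself names co-primary tests with a significance threshold, so it should say what counts as success.

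**A three-group test may suit the design better.** Arm C adds text feedback and an active nudge to what Arm B receives, so unequal effects are plausible, and the last two rows of the power table show what pooling could then lose. This stands in full. A reader might infer that Section 9 should change because the pooled test is generally more powerful; the calculations do not support that. The ground for change is that Section 3.1 names the pooled contrast as primary.

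**The Tukey step may already protect against error.** In part it does: if an intervention-control pair were required, the risk would be near or below 5% under the assumed responses. Section 9 does not require one.

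**Conclusion.** The point holds in two parts. First, the primary contrast stated in Section 3.1 has no test in Section 9, whose test is exploratory under Section 3.3; this rests on the text alone. Second, there is no one-or-both rule and no adjustment across the two questions. The false-positive risk then depends on an unstated choice:

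- either question counts: about 8-9.5% at correlations 0.3-0.8, 9.75% if independent;
- either question counts and a Tukey intervention-control pair is needed: about 3.5-5.6%, depending on log-transformation, under the assumed responses;
- both required: at most 5%.

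The 9.75% needs only independence and tests that hold their 5% level. The other ranges rest on the assumed correlations, and the Tukey range also on the response shape.

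A reader might infer that the trial runs at nearly 10% error, or that the three-group test causes the excess. The documents support neither: the excess arises only if one question is enough, which they do not say, and the pooled test gives nearly the same figure.

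**What to change.** In Section 9, before analysis:

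1. Take each primary p-value from a rank test of pooled B + C versus A, matching Section 3.1. Keep the three-group Kruskal-Wallis test and Tukey pairs as exploratory, matching Section 3.3.
2. Adjust the two primary p-values by Holm or Hochberg at family-wise 0.05. If co-primary is meant as both required, state that rule instead.

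This takes about two sentences and no new data. The price is power. The figures below assume a 0.6 SD shift in both B and C, correlation 0.5 and the pooled test:

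- Holm, effect on one question only: 82% falls to 74% at 42 per arm (65.5% to 54.5% at 28).
- Both required, effect on both: about 72% at 42 per arm (49% at 28). An effect on one question alone then supports no claim.

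The pooled primary test also loses power to show benefit over control if B and C effects differ markedly. If the investigators consider that likely and prefer the three-group test as primary, Sections 3.1 and 3.3 should be changed to say so; step 2 is needed either way.
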